9.6.2 Secondary Outcomes

Secondary Outcome Measure A: *To determine the effect of active, inhibitory rTMS (cTBS) over L-DLPFC on modulating the activity and connectivity of the neural network that underlies the hypnotic state.*

This study is designed to measure the change in hypnotic intensity by contrasting the BOLD activity(133), TMS-BOLD activity(130), and functional connectivity(133) between the L-DLPFC and dACC at pre- and post-rTMS time-points for both rTMS conditions (active L-DLPFC rTMS (cTBS) and sham L-DLPFC rTMS (cTBS))(31).

Hypnosis Scans for Secondary Outcome Measure A: All participants will receive the same identical pre-rTMS resting state scan(31, 51). After randomization (to either active DLPFC rTMS or sham rTMS) where one half (n=45) will receive active DLPFC rTMS (spaced cTBS), and one-half sham DLPFC rTMS (spaced cTBS) (n=45)(30), all participants have their hypnotizability post-rTMS scan session(31, 51).

fMRI Preprocessing and Analysis: All fMRI data will be preprocessed and analyzed using FSL (FMRIB Software Library, version 5.0) (88) and in the manner described in the Primary Outcome. For group analysis, FMRIB's local analysis of mixed effects will be used within a mask of our a priori ROIs ACC and DLPFC, thresholded using family-wise error (FWE) corrected $Z > 2.3$; cluster $p < 0.05$. Average contrast of parameter estimate values will be extracted from our ROIs and Spearman's correlations will be calculated between these values and differences in active versus sham rTMS.

Secondary Hypothesis A: *Active, inhibitory rTMS (cTBS) over L-DLPFC will modulate the neural network that underlies hypnosis by producing greater increases in activity and functional connectivity between L-DLPFC and dACC.*

Connectivity between L-DLPFC and dACC will be assessed with resting state functional connectivity MRI(31, 51) at the baseline time-point and as well as at the post-rTMS time-point for both rTMS conditions (active and sham cTBS). Analyses will be restricted to the dACC and L-DLPFC for this Secondary Outcome Measure. To determine if rTMS condition during the hypnotic state is specifically associated with change in dACC and DLPFC activity and functional connectivity, a mask restricted to dACC and DLPFC will be utilized to extract the fMRI activity and connectivity data. It is expected that the correlation in active rTMS group over L-DLPFC to be stronger than the correlation obtained in the sham rTMS group. Regression analysis will determine the strength of the relationship between the reductions of fMRI activity between dACC and L-DLPFC during the active versus sham rTMS conditions. Regression analysis will be used to investigate whether greater connectivity will be present between L-DLPFC and dACC for active rTMS versus sham rTMS.

Secondary Outcome Measure B: *To determine the effect of active, inhibitory rTMS (cTBS) over L-DLPFC on enhancing hypnotizability (as measured by the Hypnotic Induction Profile-HIP and Stroop Task) and hypnotic intensity (as measured by the Hypnotic Intensity Scale-HIS).*

Augmenting hypnosis with active rTMS may potentially produce an intervention that works better (i.e. deeper hypnotic state) and/or extends to a larger part of the population (makes more of the population hypnotizable)(26).

Hypnosis Related Measures: All participants will receive a baseline Stroop task, HIP, and HIS. After randomization (to either active DLPFC rTMS or sham rTMS) where one half (n=45) will receive active rTMS (cTBS), and one-half sham rTMS (cTBS) (n=45)(30), participant will be placed back in scanner and their HIS will be reassessed. After the post-rTMS scans, all participants will be reassessed with the Stroop task and the HIP.

Analysis of Measures: Changes in HIP, Stroop Effect, and HIS between active DLPFC rTMS and sham rTMS conditions will be compared using ANOVA. It is expected that there will be a significantly greater mean increase in HIP, HIS, and Stroop Effect with active rTMS condition than with the sham rTMS condition at the $p < 0.05$, level.

Secondary Hypothesis B: *Active, inhibitory rTMS over DLPFC will increase hypnotizability and hypnotic intensity as compared to sham rTMS.*

There are four decades of research on the effects of psychopharmacology on hypnotizability suggesting that while hypnotizability is a trait, it can be modified for the duration of the intervention(70). It is hypothesized that inhibitory left DLPFC rTMS (cTBS) will increase hypnotizability. It is expected that there will be a significant change in the pre-rTMS to post-rTMS HIP scores. It is hypothesized that the change in hypnotic depth (pre-rTMS to post-rTMS) achieved will be greater for the active rTMS group over the sham rTMS group given the early pilot work that has already been performed(26). It is expected that there will be a significantly greater mean increase in hypnotizability ratings with active rTMS than with the sham rTMS condition at the $p < 0.05$, level.

Secondary Objective C: *To determine the effect of active, inhibitory rTMS (cTBS) over L-DLPFC on the neural network underlying the conflict regulation system as a reflection of effective modulation of the neural circuitry underlying hypnotizability.*

It has been demonstrated that high hypnotizables recruit the right inferior frontal gyrus (rIFG) during conflict tasks while lows recruit the attentional network(32). Inhibitory rTMS has been demonstrated to not only modulate the hypnosis circuitry, but also change the manner in which the brain attends to stimuli(61).

Hypnosis Scans for Secondary Outcome Measure C: All participants will receive the same identical pre-rTMS Stroop task scan(32). After randomization (to either active DLPFC rTMS or sham rTMS) where one half (n=45) will receive active DLPFC rTMS (cTBS), and one-half sham DLPFC rTMS (cTBS) (n=45)(30), all participants have their post-rTMS Stroop task scan session(32).

fMRI Preprocessing and Analysis: All fMRI data will be preprocessed and analyzed using FSL (FMRIB Software Library, version 5.0) (88) and in the manner described in the Primary Outcome Measure. For group analysis, FMRIB's local analysis of mixed effects will be used within a mask of our a priori ROIs rIFG, DMN nodes, and attentional network nodes, thresholded using family-wise error (FWE) corrected $Z > 2.3$; cluster $p < 0.05$. Average contrast of parameter estimate values will be extracted from our ROIs and Spearman's correlations will be calculated between these values and differences in active versus sham rTMS.

Secondary Hypothesis C: *Active, inhibitory rTMS (cTBS) over L-DLPFC will modulate the neural network that underlies conflict regulation by producing greater activity in rIFG as well as increases in functional connectivity between the right inferior frontal gyrus (rIFG) and the default mode network (DMN) as compared to sham rTMS (sham cTBS).*

Connectivity between rIFG and DMN will be assessed with BOLD and resting state functional connectivity MRI at the baseline time-point and as well as at the post-rTMS time-point for both rTMS conditions (active and sham)(32). It is expected that the stimulation-induced functional connectivity between these the rIFG and the DMN would be increased compared to change in the connectivity in those receiving sham rTMS. It is hypothesized that inhibitory rTMS (cTBS) to L-DLPFC will result in increased fc between the rIFG and the DMN as well as increased activity in rIFG(32).

Analyses will be restricted to the rIFG and the nodes of the DMN for this Secondary Outcome Measure(32). To determine if rTMS condition during the hypnotic state is specifically associated with change in rIFG and DMN activity and functional connectivity, a mask restricted to rIFG and DMN will be utilized to extract the fMRI activity and connectivity data(32). It is expected that the correlation in active rTMS group over L-DLPFC to be stronger than the correlation obtained in the sham rTMS group. Regression analysis will determine the strength of the relationship between the reductions of fMRI activity between dACC and L-DLPFC during the active versus sham rTMS conditions. Regression analysis will be used to investigate whether greater connectivity will be present between rIFG and DMN for active rTMS versus sham rTMS.

Secondary Objective D: *To determine the effect of active, inhibitory rTMS (cTBS) over L-DLPFC on the neural network underlying the post-hypnotic suggestion Stroop Effect.*

Post-hypnotic suggestion of word-blindness eliminates the Stroop effect in high hypnotizables(119). High hypnotizables demonstrate reduced conflict signaling during the Stroop task after the post-hypnotic suggestion of word-blindness(35).

Hypnosis Scans for Secondary Outcome Measure D: All participants will receive the same identical pre-rTMS post-hypnotic suggestion Stroop task scan(35). After randomization (to either active DLPFC rTMS or sham rTMS) where one half (n=45) will receive active DLPFC rTMS (cTBS), and one-half sham DLPFC rTMS (cTBS) (n=45)(30), all participants have their post-rTMS post-hypnotic suggestion Stroop task scan session(35).

fMRI Preprocessing and Analysis: All fMRI data will be preprocessed and analyzed using FSL (FMRIB Software Library, version 5.0) and in the manner described in the Primary Outcome Measure. For group analysis, FMRIB's local analysis of mixed effects will be used within a mask of our a priori ROIs ACC and DLPFC, thresholded using family-wise error (FWE) corrected $Z > 2.3$; cluster $p < 0.05$. Average contrast of parameter estimate values will be extracted from the ROIs and Spearman's correlations will be calculated between these values and differences in active versus sham rTMS.

Secondary Hypothesis D: Post-hypnotic instruction of word blindness after active, inhibitory rTMS (cTBS) over L-DLPFC will reduce dACC activity during the Stroop task (similar to high hypnotizables) as compared to sham rTMS (sham cTBS).

Activity in dACC will be assessed with fMRI(35) at the baseline time-point and as well as at the post-rTMS time-point for both rTMS conditions (active and sham). Long-lasting (~1 hour) inhibitory rTMS (spaced continuous theta-burst stimulation approach(30)) will be applied to L-DLPFC and expect that the stimulation-induced functional connectivity between these two nodes would be increased as a surrogate of increased hypnotizability and therefore increased post-hypnotic Stroop Effect.

Analyses will be restricted to the dACC and DLPFC for this Secondary Outcome Measure. To determine if rTMS condition during the hypnotic state is specifically associated with change in dACC and DLPFC activity, a mask restricted to dACC and DLPFC will be utilized to extract the fMRI activity. The correlation in active rTMS group over L-DLPFC is expected to be stronger than the correlation obtained in the sham rTMS group. Regression analysis will determine the strength of the relationship between the reductions of fMRI activity between dACC and L-DLPFC with active versus sham rTMS conditions.

Secondary Outcome E: *To determine the effect of active, inhibitory rTMS over DLPFC on modulating the neural network that underlies hypnotic analgesia.*

This aim explores if L-DLPFC rTMS modulated increase in hypnotizability will have downstream effects on the hypnotic analgesia modulation of the rest of the hypnotic analgesia network (ACC, insula and/or the somatosensory cortex) by strengthening the activations/deactivations induced by HA as well as strengthening the functional connectivity induced by HA.

Hypnosis Scans for Secondary Outcome Measure D: The participants will have a baseline scan with baseline pain induction in the scanner. For this scanning session, task fMRI data will be collected while participants are randomized to receive and rate painful thermal stimulations after either active rTMS (cTBS) + hypnotic analgesia (HA) or sham rTMS + hypnotic analgesia. The differences in pain ratings and regional brain activity of the networks related to hypnotic analgesia (restricted to masks of the insula, somatosensory, L-DLPFC, and anterior cingulate cortices) as well as analyzing the functional connectivity changes between dACC and the L-DLPFC, insula, somatosensory cortices as well as between L-DLPFC and the dACC, insula, and somatosensory cortices will be analyzed. Given the relative mechanistic independence of these two putative interventions (rTMS and HA)(37, 68), it is possible that active rTMS would also directly affect analgesia, although unlikely given stimulation frequency. Certainly the downstream neural network effects of both interventions have overlapping and non-overlapping brain regions that are specific to the intervention(37, 68). rTMS, however, has been demonstrated to reach what were previously thought to be non-connected regions of a given neural network in a given condition or state(46). It is possible that rTMS alone may activate certain network nodes in one state, but in a different mental state activate other network nodes(125). This study strives to determine if rTMS modulation of hypnotizability can produce the downstream effect of increasing functional connectivity and decreasing activation of anterior cingulate, insular, and somatosensory cortices, which are areas involved in the HA network(37).

fMRI Preprocessing and Analysis: All fMRI data will be preprocessed and analyzed using FSL (FMRIB Software Library, version 5.0) and in the manner described in the analysis description for the Primary Outcome Measure. For group analysis, FMRIB's local analysis of mixed effects will be used within a mask of our a priori ROIs (L-DLPFC, dACC, insula, and somatosensory cortices), thresholded using family-wise error (FWE) corrected $Z > 2.3$; cluster $p < 0.05$. Average contrast of parameter estimate values will be extracted from our ROIs and Spearman's correlations will be calculated between these values and differences in active versus sham rTMS.

Secondary Hypothesis E: *Active, inhibitory rTMS over DLPFC will modulate the neural network that underlies hypnotic analgesia by producing a decrease in activity and an increase functional connectivity among the anterior cingulate, dorsolateral, insular, and somatosensory cortices (hypnotic analgesia network) as compared to sham rTMS.*

The neural network involved with HA (anterior cingulate, dorsolateral prefrontal, insular, and somatosensory cortices) will be assessed at baseline (after pre-TMS hypnotic analgesia instruction) hypnosis and after rTMS (again after hypnotic analgesia instruction). Activation/deactivation as well as connectivity between baseline and post-TMS will be contrasted to determine if only the active rTMS condition results in greater reductions of activity within the network involved in hypnotic analgesia(6, 37) in comparison to sham rTMS. Changes in activity and connectivity between baseline scan and HA + active DLPFC rTMS and HA + sham rTMS conditions will be compared using ANOVA. We expect a significantly greater mean decrease in

activity and increase in connectivity with the HA + active rTMS conditions than the HA + sham rTMS condition at the $p < 0.05$, level.

Analyses will be restricted to the anterior cingulate, L-DLPFC, insular, and somatosensory cortices. The correlation in the active rTMS + HA condition is expected to be stronger than the correlation obtained in the sham rTMS + HA. To determine if a given rTMS condition is specifically associated with HA induced change in that stimulated L-DLPFC activity, a mask restricted to dACC, DLPFC, insula and somatosensory cortex will be utilized to extract the fMRI activity data. Regression analysis will determine the strength of the relationship between the reductions of fMRI activity within the hypnotic analgesia network(4, 19) during the active versus sham rTMS conditions. Regression analysis will be used to investigate whether greater activity and connectivity will be present in the HA network (anterior cingulate, L-DLPFC, insular, and somatosensory cortices) for active rTMS-augmented hypnotic analgesia versus hypnotic analgesia alone (sham rTMS).

Secondary Outcome Measure F:

F.1. To evaluate cortical excitatory and inhibitory neurotransmitters, 1H-MRS will be acquired to determine the concentrations of GABA and glutamate/glutamine (Glx).

F.2. We will evaluate the associations between neurotransmitter levels and functional connectivity as well as behavioral measures of clinical pain level and duration.

F.3. As an exploratory aim, we will acquire a broad spectra MRS scan to determine dysregulation in other neurometabolites, particularly myo-inositol - a marker of neuroinflammation linked to glial reactivity.

Secondary Hypothesis F: *L-DLPFC GABA levels will be negatively associated with clinical pain measures in participants with FMS.*

MRS Analysis:

GABA and Glx Spectra Analysis GABA and Glx MRS will be analyzed using Gannet software implemented within MATLAB. Analysis will be conducted in two principal stages: 1) processing of raw time-domain data from the scanner into GABA-edited frequency-domain difference (DIFF) spectra with the following steps – line broadening, zerofill, fast Fourier transform, and extraction of water frequency; 2) Spectra fitting to quantify the edited GABA signals. To perform GABA J-difference editing two acquisitions will be acquired differing in the manipulation of the GABA spin system. Subsequent subtraction of the manipulated acquisitions will reveal GABA signals under the more prominent creatine (Cr) signal at 3 ppm. Next difference editing will be applied by subtracting the larger Cr signal to identify the smaller GABA signal. Next, Cr signal frequency-domain fitting will occur in the editing-OFF spectra. This will be conducted because the small GABA signal is susceptible to magnet instabilities including scanner drift and experimental quandaries such as subject movement. Quantification of GABA spectra will be obtained by applying a Gaussian model with linear baseline to the GABA signals in the DIFF spectra constrained within frequencies from 2.8 to 3.6 ppm, a Lorentzian model for the Cr signals in the OFF spectra constrained between 2.7 and 3.1 ppm, and a GaussianLorentzian model for the unsuppressed water spectrum constrained between 2.8 and 3.6 ppm. The resulting outputs include the integral ratio of GABA relative to Cr, GABA concentration relative

to water in institutional units (i.u.). Glx ratio will be derived from LCModel version 6.3-1 software using a simulated basis set, the jMRUI Amares algorithm in a similar method described by O’Gorman and colleagues [178]. Integration of the co-edited Glx signal at 3.75 ppm will be carried out using a linear fit to the baseline and the sum of two Lorentzians to fit the doublet peak. A regression and/or correlation analysis will be used to determine the relationship between changes in connectivity, MRS and behavioral metrics (clinical pain measures and hypnotizability). We will include regressors of non-interest for time between study visits, sex, and age.

Secondary Outcome Measure G:

G.1. Using MRS, we will evaluate the L-DLPFC GABA concentrations before and after cTBS in a double-blinded sham-controlled design. The cartesian coordinate of the L-DLPFC cTBS target will be used for MRS voxel placement. As an internal control, right DLPFC MRS will be acquired for each subject to distinguish the laterality of the hypnosis effect.

Aim G.2. We will test whether changes in functional connectivity and behavioral measures of hypnotizability and hypnotic analgesia are associated with alterations in GABA MRS concentration.

Secondary Hypothesis G: *cTBS neuromodulation of L-DLPFC-dACC connectivity is mediated by inhibitory inter-neuronal cortical pathways measured by GABA MRS in the L-DLPFC. Neuromodulation induced by TMS has been shown to increase L-DLPFC-dACC connectivity, but the neurochemistry underlying these changes is unknown.*

MRS Analysis:

MRS analysis will be conducted identical to the Secondary Outcome Measure F. A subtraction of metabolic concentrations between pre- and post-TMS sessions will be used for subsequent correlation between changes in hypnotic analgesia and clinical pain measures. After completion of the study, unblinded data will be used to determine active versus sham changes in metabolic concentrations.

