1.2 Secondary Objectives

Secondary Objective A: *To determine the effect of active, inhibitory rTMS (cTBS) over L-DLPFC on modulating the neural network that underlies hypnotic intensity.*

Secondary Hypothesis A: *Active, inhibitory rTMS (cTBS) over L-DLPFC will modulate the neural network that underlies hypnotic intensity by decreasing activity in L-DLPFC and dACC as compared to sham rTMS (sham cTBS) as measured by BOLD fMRI and interleaved TMS-MRI.*

Secondary Objective B: *To determine the effect of active, inhibitory rTMS (cTBS) over L-DLPFC on enhancing hypnotizability (as measured by the Hypnotic Induction Profile-HIP and Stroop Task) and hypnotic intensity (as measured by the Hypnotic Intensity Scale-HIS).*

Secondary Hypothesis B: *Active, inhibitory rTMS (cTBS) over L-DLPFC will increase the HIP and HIS scores as well as hypnotic reduction of the Stroop Effect as compared to sham rTMS (sham cTBS).*

Secondary Objective C: *To determine the effect of active, inhibitory rTMS (cTBS) over L-DLPFC on the neural network underlying the conflict regulation system as a surrogate of effective modulation of the neural circuitry that underlies hypnotizability.*

Secondary Hypothesis C: *Active, inhibitory rTMS (cTBS) over L-DLPFC will modulate the neural network that underlies conflict regulation by producing greater increases in functional connectivity between the right inferior frontal gyrus (rIFG) and the default mode network (DMN) as compared to sham rTMS (sham cTBS).*

Secondary Objective D: *To determine the effect of active, inhibitory rTMS (cTBS) over L-DLPFC on the neural network that underlies the post-hypnotic Stroop Effect.*

Secondary Hypothesis D: *Post-hypnotic instruction of word blindness after active, inhibitory rTMS (cTBS) over L-DLPFC will reduce dACC activity during the Stroop task (similar to high hypnotizables) as compared to sham rTMS (sham cTBS).*

Secondary Objective E: *To determine the effect of active, inhibitory rTMS (cTBS) over L-DLPFC on modulating the neural network that underlies hypnotic analgesia (HA).*

Secondary Hypothesis E: *Active, inhibitory rTMS (cTBS) over L-DLPFC will modulate the neural network that underlies HA by producing a decrease in activity and an increase functional connectivity among the anterior cingulate, dorsolateral, insular, and somatosensory cortices (hypnotic analgesia network) as compared to sham rTMS (sham cTBS).*

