Validity of the Approach: It has been previously demonstrated that inhibitory rTMS over the L-DLPFC can modulate the level of hypnotizability of the subject (26). Because rTMS has been demonstrated to affect hypnotizability and it is suspected that rTMS (26) will therefore affect hypnotic intensity (133). It has been demonstrated that rTMS can manipulate the Stroop effect bi-directionally, in a frequency-dependent manner (118, 153, 154). It has also been demonstrated that performance on conflict tasks such as the Stroop task and the flanker task are correlated with hypnotizability (32).

Reliability of the Approach: It has been demonstrated across numerous studies that rTMS is capable of modulating cognitive tasks in a frequency-dependent manner (155-157).

Secondary Objective C: To determine the effect of active, inhibitory rTMS (cTBS) over L-DLPFC on the neural network underlying the conflict regulation system as a reflection of effective modulation of the neural circuitry underlying hypnotizability.

Secondary Hypothesis C: Active, inhibitory rTMS (cTBS) over L-DLPFC will modulate the neural network that underlies conflict regulation system by decreasing activity in right inferior frontal gyrus (rIFG) and the connectivity of the rIFG to the default mode network (DMN).

Validity of the Approach: Difference in hypnotizability has been correlated with difference in neural strategy for conflict tasks such as the Stroop task and the flanker task (32).

Reliability of the Approach: It has been demonstrated that both the BOLD and functional connectivity measures are reliable across numerous studies (51).

Secondary Objective D: To determine the effect of active, inhibitory rTMS (cTBS) over L-DLPFC on the neural network underlying post-hypnotic Stroop Effect.

Secondary Hypothesis D: Post-hypnotic instruction of word blindness after active, inhibitory rTMS (cTBS) over L-DLPFC will reduce dACC activity during the Stroop task (similar to high hypnotizables) as compared to sham rTMS (sham cTBS).

Validity of the Approach: It has been demonstrated that a post-hypnotic instruction of word blindness will produce a loss of the Stroop Effect in highly hypnotizable individuals (119, 120). It has also been demonstrated that the loss of the Stroop Effect is correlated with reduction in conflict signaling in the dorsal anterior cingulate (35).

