9.2 Sample Size and Randomization

For the power estimation, this study will use the significance level of .05 with two-tailed test. This study will recruit 100 individuals assuming about 20% missing data due to unusable imaging data and dropouts. In the Primary Mechanistic Hypothesis (formerly connectivity portion of Hypothesis 1a), power was estimated by focusing on the functional connectivity between DLPFC and dACC as the Primary Mechanistic Outcome. According to one prior study (47), the change in connectivity between DLPFC and dACC from pre to post rTMS is change in the quite large ($d=0.69$). We have augmented this one finding with numerous findings from other rTMS connectivity and functional activity studies, which demonstrated quite large effect sizes (see table 3 and table 4 below). Therefore, a somewhat conservative effect size of $d=0.8$ is being utilized for this study. The change from baseline to post-stimulation will be negligible in the sham rTMS group. Given this scenario, with the usable sample of 80 (40 rTMS, 40 sham), the estimated power is 0.8 ($\alpha=.05$, two-sided). For the Relevant Clinical Hypothesis (formerly Hypothesis 2b) and Secondary Hypotheses E (formerly Hypothesis 2a) as well as Secondary Hypotheses A, C, and D, both effect sizes and p-values will be monitored, with more emphasis on gathering information on effect sizes.

Manuscript	Site of Stimulation	Functional Connectivity Pair	Effect Size
Eldaief et al	L Posterior Intraparietal Lobule	rpIPL<->mPFC	0.72
Eldaief et al	L Posterior Intraparietal Lobule	rpIPL<->PCC	0.62
Nettekoven	Primary motor cortex	Primary Motor Cortex<->Premotor Cortex	0.9
Halko et al	Lateral cerebellum	DMN<->Posterior cingulate	1.26
Valchev et al	Primary somatosensory	Premotor	0.79

Vercammen Watanabe et al	Temporal-Parietal-Junction	Temporal-Parietal-Junction<->Right Insula	1.33
Watanabe et al	Left Motor Cortex	Left Motor Cortex<-> Right Motor Cortex	1.79
Watanabe et al	Left Motor Cortex	Left Motor Cortex<-> Right Motor Cortex	2

Table 3: Effect sizes for rTMS induced changes in functional connectivity as a surrogate for hypnotizability (Hoeft 2012)(31) modulated by rTMS(54, 56, 57, 158-160).

Manuscript	Stimulation Site	MRI/PET	Effect Size
Hubl	Frontal Eye Field	BOLD	0.4242
Bestmann	Motor/Somatosensory cortex	BOLD	2.36686405
Bestmann	Motor/Somatosensory cortex	BOLD	2.30589176
Cho	Right Dorsolateral prefrontal cortex	PET (CBF)	1.70333333

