It is hypothesized that the rTMS modulation in hypnotizability(26) will result in greater hypnotic analgesia than sham rTMS. It is expected that a significantly greater mean increase across measures active rTMS than with the sham rTMS condition at the $p < 0.05$, level. This hypothesis will be tested with linear mixed modeling. It is hypothesized that the rTMS modulation will result in greater analgesia than sham rTMS. This study will measure the response to thermal pain stimuli at baseline and after active rTMS versus sham rTMS. In particular, it is hypothesized that the temperature necessary to produce threshold level heat pain during the pre-TMS period will not produce pain following active rTMS + HA. The temperature for evoking threshold and moderate pain will be assessed prior to and at 5-minute intervals for 30 minutes following the application of rTMS + HA. It is expected that the active rTMS stimulation + HA will temporarily eliminate pain following thermal stimulation at an intensity, which produced threshold level pain prior to rTMS + HA. It is also hypothesized that temperatures that produced moderate pain prior to rTMS will be significantly reduced following active rTMS versus sham. This hypothesis will be tested with linear mixed modeling and changes $p < .05$ are considered statistically significant.

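### Secondary Hypothesis C, the activity part of A and the Stroop part of B are each stated with opposite signs in different places, so a significant result either way could be presented as predicted

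*Combined protocol and SAP*

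**What the plan says.** All places are in the combined protocol and SAP unless stated.

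- **Hypothesis C.** Section 9.1 says active rTMS acts "by decreasing activity in right inferior frontal gyrus (rIFG) and the connectivity of the rIFG to the default mode network (DMN". Section 9.6.2 has it "producing greater activity in rIFG as well as increases in functional connectivity between the right inferior frontal gyrus" and the DMN. Sections 1.2 and 3 predict increased rIFG–DMN connectivity and do not mention rIFG activity.
- **Hypothesis A.** Sections 1.2 and 9.1 predict "decreasing activity in L-DLPFC and dACC as compared to sham rTMS", and section 3 predicts reduced dACC activity. The statement in section 9.6.2 is "producing greater increases in activity and functional connectivity between L-DLPFC and dACC".
- **Hypothesis B.** Section 1.2 predicts higher HIP and HIS scores and "hypnotic reduction of the Stroop Effect as compared to sham rTMS". Sections 3 and 9.1 list the Stroop effect among the things that will increase. Section 9.6.2 expects a "significantly greater mean increase in HIP, HIS, and Stroop Effect with active rTMS condition", at p < 0.05.
- **Thermal pain.** Section 9.6.1 says that "temperatures that produced moderate pain prior to rTMS will be significantly reduced following active rTMS versus sham".
- **Testing.** Under section 9.2, "this study will use the significance level of .05 with two-tailed test". Sections 9.2 and 9.7 put more weight on effect size than on significance for most of these hypotheses, but p-values are still to be examined.
- **Separate SAP (January 2024).** Its only efficacy analyses concern HIP. It says nothing on the sign of any other endpoint.

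**The concern.** Under a two-sided test, the predicted sign decides whether a significant difference supports the hypothesis or contradicts it. If the plan holds both signs and no order of precedence, an author can cite whichever section matches the result, and a reader cannot tell whether the prediction was met. Putting the emphasis on effect sizes does not remove the difficulty, because an effect size also has to be read against a predicted sign.

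At stake are secondary claims about how stimulation acts on conflict regulation (C), on the network behind hypnotic intensity (A) and on the behavioural Stroop measure (B). The primary connectivity claim is not affected.

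**Working it through.** **Step 1. Set the statements side by side.**

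| Endpoint | 1.2 | 3 | 9.1 | 9.6.2 hypothesis | 9.6.2 supporting text |
|---|---|---|---|---|---|
| C: rIFG–DMN connectivity | up | up | down | up | up |
| C: rIFG activity | – | – | down | up | up |
| A: L-DLPFC and dACC activity | down | down (dACC only) | down | up | down |
| B: Stroop effect | down | up | up | not named | up |
| B: HIP and HIS | up | up | up | up | up |
| E: analgesia-network activity | down | down | down | down | down, then up |

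- **C** is a full reversal on both measures, and no reading reconciles section 9.1 with section 9.6.2.
- **A** is one sentence against the rest. Its own analysis text speaks of reductions in activity, and the primary hypothesis in section 9.6.1 expects reduced activity in both regions.
- **B** conflicts in the Stroop component only. The term itself is unstable: sections 6.2.2 and 9.1 describe loss of the Stroop effect as the response of highly hypnotizable people, while the text under Hypothesis D in section 9.6.2 expects greater hypnotizability to increase the post-hypnotic Stroop effect. No score is defined.
- **E** predicts decreased activity throughout, but its last regression sentence looks for greater activity with active rTMS.
- **Thermal pain** conflicts within section 9.6.1. Read literally, a lower temperature for moderate pain means more sensitivity. The surrounding sentences predict that the old threshold temperature will stop being painful and that pain ratings will fall. The section also has that temperature re-measured at 5-minute intervals for 30 minutes, so the literal sentence is testable as written.

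**Step 2. False support when there is no effect.** Input: two-sided alpha 0.05 (section 9.2).

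- Either sign accepted: 0.05 per endpoint.
- One sign fixed, same two-sided test: 0.05 / 2 = 0.025 per endpoint.

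**Step 3. A true effect opposite to the intended one.** Inputs: 40 usable participants per arm (section 9.2); true standardized differences |d| of 0.2 to 0.8, which are assumed because the plan gives none for these endpoints; a two-group t-test on the change score with 78 degrees of freedom. The noncentrality is |d| × √(40/2) = |d| × √20, and c is the 97.5% point of t with 78 df. The chance of significance in the true direction is 1 − F(c), and in the intended direction F(−c), with F the noncentral t distribution.

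| Assumed true effect, opposite to intended | Reportable as support if either sign counts | Reportable as support if the sign is fixed |
|---|---|---|
| 0.2 | 0.14 | 0.0022 |
| 0.3 | 0.26 | 0.0005 |
| 0.5 | 0.60 | below 0.0001 |
| 0.8 | 0.94 | below 0.0001 |

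The plan's only power figure, 0.8 for the primary connectivity comparison, is not used here. With 40 per arm and d = 0.8 the same formula gives 0.94. That mismatch is a separate matter.

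**The case against.** The strongest reply is that most of this is loose drafting. Hypothesis A is a single outlying sentence, contradicted by the paragraph that follows it. Stroop effect may be shorthand for the hypnotic change in the effect. The moderate-pain sentence reads naturally as pain at those temperatures, especially as sections 6.2.2 and 6.2.5 hold the scanner temperature fixed from before to after rTMS. Secondary aims are to be judged mainly by magnitude, and no passage says that analysts would accept either sign.

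Much of that stands, and it limits the point. It does not explain Hypothesis C. Nor does it remove the need to correct A in the section that specifies its analysis, or to define the Stroop score, since the Stroop prediction carries a p < 0.05 criterion.

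A reader might go further in four ways that the documents do not support:

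- **That Hypothesis B is reversed as a whole.** HIP and HIS rise in every statement, so a fall in either could not be called confirmation.
- **That the trial predicts hyperalgesia.** Sections 1.1, 3, 9.1 and 9.6.1 all predict enhanced hypnotic analgesia.
- **That the type I error is inflated.** The nominal two-sided 0.05 is unchanged.
- **That false support across A, B, C and thermal pain is 1 − 0.95⁴ = 18.5% against 1 − 0.975⁴ = 9.6%.** This needs four independent, fully reversed claims with one test each. The documents do not support independence, and not all four are fully reversed.

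**Conclusion.** The point holds for Hypothesis C in full, for activity in Hypothesis A, and for the Stroop component of Hypothesis B. Hypothesis E and the moderate-pain sentence are slips to correct alongside them. The primary hypothesis, that L-DLPFC–dACC connectivity increases, has the same direction in sections 1.1, 3, 9.1 and 9.6.1.

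The harm is lost falsifiability of secondary claims. Its size is 5% instead of 2.5% false support per affected endpoint under no effect, on the condition that either sign would be accepted as support. A real effect in the unintended direction could also be presented as confirmation, with the chances shown above. Those chances rest on assumed effect sizes, 40 per arm and a simple two-group comparison; they do not describe the cluster-thresholded imaging maps. This should be corrected, but it does not threaten the primary result.

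**What to change.** - Keep the two-sided tests.
- For each endpoint state region, contrast and predicted sign once, and use it identically in sections 1.2, 3, 9.1 and 9.6. This covers rIFG activity, rIFG–DMN connectivity, L-DLPFC and dACC activity, and analgesia-network activity.
- Define the Stroop score, for example incongruent minus congruent interference, and say which sign means a greater hypnotic effect.
- Reword the moderate-pain sentence in section 9.6.1 to agree with the pain-rating and threshold predictions around it.
- State that a significant result with the opposite sign will be reported as contrary to the hypothesis.

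Sample size, tests and data collection do not change. Timing is the real cost. The January 2024 SAP reports in the past tense that data were collected and HIP scores examined, and neither document shows whether the imaging and Stroop analyses had been done. Where unblinded analysis of an endpoint has not begun, fix and date the sign first. Where it has, a direction chosen now cannot be shown to be prespecified, and the report should disclose that both directions were on file.
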